The overall goal for this study is to evaluate the efficacy of a group-treatment integrating VR and CBT (TREATMENT group), compared with a tailored home-exercise program with telephone follow-up (CONTROL group) in persons with persistent dizziness.

Hypothesis:

Participants receiving the Vestibular Rehabilitation and Cognitive Behaviour Therapy (VR-CBT) programme will show significantly superior reduction in perceived dizziness related handicap in addition to increased preferred gait velocity, compared with persons completing a home-exercise program with telephone follow-up.

SECTION 3: TRIAL METHODS

9. Brief description of trial design

The study is designed as an assessor-blinded randomised controlled superiority trial with a two-group parallel design. All participants received a brief Intervention Vestibular rehabilitation session (BI-VR) (see study-protocol (1)) before being randomised, using block randomisation (with 16 participants in each block), into either CONTROL (home-exercises) or TREATMENT (VR-CBT) group.

All included participants went through baseline assessment comprising physical examination outcome measures and self-reported questionnaires. Prior to randomisation all participants received an individual one-hour BI-VR session with a physiotherapist. The session included physical examination, information regarding the vestibular system and possible causes of dizziness, advice related to findings, all with the intention of reducing fear of movement. In

addition, the participants were supervised in selected VR exercises related to their complaints. All participants were advised to be active. After the BI-VR session, the participants were randomised into a CONTROL or TREATMENT group.

The participants allocated to CONTROL were encouraged to work with the exercises prescribed by the BI-VR physiotherapist, and to stay active. The physiotherapist offered two telephone consultations during a 4-month period to encourage compliance with home-exercises and answer questions that may have arisen.

The participants allocated to TREATMENT group attended a structured group-treatment program (VR-CBT). Each group included five to eight participants attending weekly group sessions for 8 weeks. Each session lasted 2 hours and was led by two physiotherapists, integrating VR and CBT following an established treatment manual.

The primary endpoints will be the between group difference in change of dizziness related handicap and preferred gait velocity from baseline to 6 and 12 months follow up.

The study has two primary outcomes:

Dizziness-related handicap is measured using the Dizziness Handicap Inventory (DHI). The DHI is designed to quantify the perceived impact of dizziness and unsteadiness. It contains 25 questions, each item has 3 alternative scores “0” (no), “2” (sometimes) and “4” (yes), giving a score range of 0 to 100 DHI points (8).

Preferred gait velocity is used as a measure of functional level. The participants are asked to walk down an 8-meter pathway, timed in the middle 6 meters. The trial is timed using a stopwatch, from when the first foot passes the start point, to where the last foot passes the stop point. The mean velocity over two trials is calculated and presented in m/s.

A more detailed description of the study is presented in the protocol (1).

10. Randomisation and blinding.

After BI-VR the participants were block-randomised (in blocks of 16) into two groups, the CONTROL or TREATMENT group (Group A or B). Group allocations were performed using a random number generator and presented in a concealed envelope after completing the BI-VR. After breaking the code, the BI-VR therapist and the participants were aware of group allocation, while the assessor, also analysing the data, remained blinded. Prior to testing at 6- and 12-months participants were reminded not to divulge group allocation.

Prior to breaking the blinding, the authors of this SAP will agree on how to interpret the results on the bases of a blinded review of the data from the primary endpoints. Two possible interpretations will be made. One assuming that group A was in the treatment group, and the other assuming that group B was in the treatment group. When all authors have agreed to the interpretations, the randomisation code may be open. This procedure is conducted to reduce bias in the interpretation of the results.

11. Sample size calculation

The sample size calculation was based on the between group difference in the mean change scores of the total DHI score and the preferred gait velocity. As two primary outcomes were chosen for the study power and sample size calculation was calculated for both outcomes (1). In order to obtain a clinically important group difference in the DHI of 11 points (9), with a significance level of 0.05 and a power of 80% (SD 18.95), 47 participants are required per group. In order to obtain a clinically important group difference in preferred gait velocity of 0.1 m/s (10, 11) with a significance level of 0.05 and a power of 80% (SD 0.15), 36 participants are required per group.

Therefore, the larger sample size of 47 in each group was used, resulting in at least 94 participants. To reduce the risk of dropouts affecting the analyses the preferred sample size was set to 124 participants, allowing for a conservatively estimated drop-out rate of 24%.

12. Description of hypothesis testing framework

All outcomes will be analyzed using a superiority framework, expecting that participants attending TREATMENT group will improve more than participants in the CONTROL group.

13. Planned interim analyses and stopping guidance

The published study protocol suggested possible interim analyses to adjust sample size. Apart from that no formal stopping guidelines or interim analyses were planned.

14. Details of timing of analyses

Participants were assessed at baseline, with follow-up testing after approximately 6 and 12 months. All analysis will be analysed after final data-collection. The primary outcomes will be analysed by a blinded biostatistician. The secondary outcomes will be analysed by LK. Data from baseline, 6- and 12-months follow-up will be included in these analyses. All primary and selected secondary outcomes presented at www.clinicaltrials.gov (NCT02655575) will be presented in the primary or subsequently secondary reports.

15. Timing of outcome assessments

Table 1. An overview of the different stages of the study, with a presentation of outcomes and their timepoint for testing.

Timepoint	STUDY PERIOD			
	Enrolment	Post-allocation		
	Month 0-2	Month 1-6	6 months	12 months
ENROLMENT				
Eligibility screen	X			
Informed consent	X			
Allocation		X		
INTERVENTIONS				
BI-VR		X		
VR-CBT/ Home exercises			X	
ASSESSMENTS				
Initial questionnaire and demographics	X			
Clinical dynamic visual acuity	X			
Grip strength	X			
PRIMARY OUTCOMES				
Dizziness Handicap Inventory	X		X	X
Preferred gait velocity	X		X	X
SECONDARY OUTCOMES				
Physical tests				
Fast gait velocity	X		X	X
Elements from GPE	X		X	X
Dual task walking	X		X	X
Body sway	X		X	X
Head movement induced dizziness	X		X	X
Questionnaires				
Mobility Index, Alone	X		X	X
Body Sensation Questionnaire	X		X	X
Agoraphobic Cognition Questionnaire	X		X	X
Panic Attack Scale	X		X	X
Hospital Anxiety and Depression Scale	X		X	X
Vertigo Symptom Scale- Short form	X		X	X
Chalders fatigue questionnaire	X		X	X
EQ5D-5L	X		X	X
Subjective Health Complaints	X		X	X
Patient Global impression of Change			X	X

SECTION 4: STATICAL PRINCIPLES

Confidence intervals and p-values

16: Level of statistical significance and confidence intervals

All statistical tests carried out to assess the between-group effects, will consist of two-sided tests with a 95% confidence level ($p < 0.05$).

17: Adjustment for multiplicity

Since this study has two primary outcomes post-hoc analysis the Holm-Bonferroni method will be used to control for a possible Type 1 error.

18. Confidence intervals

All confidence intervals presented will be 95% and two-sided.

Adherence and protocol deviations

19.a. Definition of adherence to the intervention

Satisfactory adherence for the VR-CBT group was predefined as attending 6 of the 8 group treatment sessions (75%), and completion of at least 80% of the exercise diaries, where 100% was predefined as reporting exercising and following the walking program 5 times per week. Satisfactory compliance in the control group was predefined as completion of at least one phone call with the BI-VR therapist (1).

19.b. Description of how adherence will be presented

The adherence will be presented as the number and percentage of participants achieving satisfactory adherence (described above). For the intervention group the adherence to group attendance and home-exercises will be presented separately.

19c & 19d. Definition of protocol deviations and how they will be reported

Major deviations from adherence to protocol is defined as:

- Less than 50% attending more than 75% of the VR-CBT treatment.
- Less than 50% completing at least one follow-up telephone call.

All major protocol deviations will be reported in the primary report.

Analysis populations

20. Definition of analysis populations

Intention-To-Treat: Primary analyses will be conducted according to intention to treat protocol, where all participants were included according to the treatment group they were randomized into. The distribution of the primary outcomes (change score of DHI and preferred gait velocity) will be visualized using scatterplots and described by mean and 95% CI for each group.

Per protocol: In addition, analyses will be conducted on the two groups with respect to treatment adherence (See definition of good adherence section 19a). Thus, analyses will be conducted using per protocol analysis, according to this comparison:

- Participants in the CONTROL group with good adherence, and no other interventions.
- Participants in the TREATMENT groups with good adherence, and no other interventions.

SECTION 5: TRIAL POPULATION

Screening data

- 21. Reporting of screening data

The total number of possible participants screened for eligibility throughout the recruitment period (start and end date) will be reported.

Eligibility

- 22. Summary of eligibility criteria

Inclusion criteria:

- 18-70 years
- Acute onset of dizziness, with symptoms lasting at least 3 months
- Dizziness triggered/ worsened by head movements

Exclusion criteria:

- Self-reported non-vestibular reason for dizziness (e.g. neurological condition)
- Fluctuating vestibular disease (e.g. Menière's disease)
- Recently treated or organised future treatment for benign paroxysmal positional vertigo (1 month previously or in the future).
- Conditions where fast head movements are contraindicated (e.g. osteoporosis of the neck)
- Severe/ terminal pathology
- Participation of group therapy for dizziness in within the past year

- Inadequate Norwegian language proficiency (written and oral)
- Unable to attend test and treatment location.

Recruitment and withdrawals

- 23 & 24: Information to be included in the CONSORT flow diagram

The CONSORT flow diagram will consist of the following:

- All patients assessed for eligibility throughout the recruitment period
- All patients meeting one or more of the exclusion criteria, with reasons
- All patients eligible for inclusion in the trial
- All eligible patients not consenting, with reasons
- All patients randomized for both treatment arms
- All patients receiving and not receiving the allocated treatment for both treatment arms
- All patients with answered DHI questionnaire at 6- and 12-months follow-up
- All patients with registered preferred gait velocity at 6- and 12-months follow-up
- Withdrawals/lost to follow-up with reasons and timing for both treatment arms
- Patients included in the ITT and per protocol for both treatment arms

Baseline patient characteristics

- 25a: List of baseline characteristics to be summarized

Baseline data that will be presented include: Age, gender, duration of dizziness, education level, reported employment status, number of dizziness complaints, reported weekly activity level. In addition will primary and secondary outcome scores at baseline be presented.

For further details, please see the published study protocol (1).

- 25b: Details on descriptive summary of baseline characteristics

Categorical and binary data will be summarized by absolute and relative frequencies. Continuous and count data will be summarized by mean and median with standard deviation and percentiles as appropriate. In case of only few different values observed or unusual shape of the distribution (e.g. bimodality, extreme skewness), also absolute and relative frequencies will be reported, potentially after a suitable categorization. No formal tests for significant differences between groups at baseline will be performed, as this is not recommended by CONSORT.

SECTION 6. ANALYSIS

Outcome definitions

- 26. Specification of outcomes and timing.

Table 1 presents an overview of the outcomes and timing. A detailed presentation of the primary outcomes is presented in section 3, while the secondary outcomes are presented in the study protocol (1).

Analysis methods

- 27. What analysis methods will be used

All outcomes will be presented using descriptive statistics; normally distributed data by the mean and standard deviation (SD), and skewed distributions by median and interquartile range (IQR). Binary and categorical data will be presented using *counts* and percentages.

Primary outcomes:

The efficacy analysis will be based on the assessment of the between group differences in changes in DHI scores and preferred gait velocity at 6- and 12-month follow-up. A linear-mixed model with repeated measures will be applied, where group allocation (TREATMENT and CONTROL) and time (6 and 12 months) will be treated as categorical values. The estimated difference in change will be presented in group means and 95% confidence intervals with associated p-values.

Secondary outcomes

Continuous secondary outcomes will be analyzed using the same method as described above.

Missing data

- 28. Handling of missing data

The analysis will use the Intention to Treat (ITT) principle, analysing all randomised participants independent of compliance and withdrawals. In the event of missing data two methods will be used.

For missing single questions, the mean baseline value for the respected group will be assigned. If a complete questionnaire or physical outcome is missing a non-responder imputation will be used.

Loss to follow-up analyses: Dropouts are defined as those who did not complete both physical assessment and patient reported outcomes at 6- or 12-month follow-up. Multiple imputation will be utilised where data is missing.

Additional analysis

- 29. Details of any additional analysis

Additional reports may be presented on the outcomes presented at ClinicalTrials.gov (ID: NCT02655575).

Harms

- 30. Handling of adverse events

Participants may experience increased symptoms in the short term. However, serious adverse events (e.g. death, life-threatening events, disability, and permanent damage) is not anticipated. We will report the number of adverse events if present.

Statistical software

- 31. Details of statistical package used for the analysis

STATA (StataCorp, College Station, Tx, USA) will be used for the analyses.

Operation procedures

- 32. Data management

Three assessors are involved in data collection. The principal investigator will register all data into files stored on a secure server. Paper copies, where applicable, will be stored securely, only accessible by the principal investigator. Personal information will be stored separate from the main data and will not be shared by anyone outside the central study team.

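### The group therapy arm is analysed as if its participants were independent; if outcomes correlate within therapy groups, the intervals are too narrow and the type I error exceeds 5%

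*Combined protocol and SAP*

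**What the plan says.** Section 9 describes two different modes of delivery. In TREATMENT, "Each group included five to eight participants attending weekly group sessions for 8 weeks", with two physiotherapists leading each two-hour session. CONTROL participants do home exercises and are offered two telephone consultations. Participants are randomised individually.

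Section 27 specifies a linear mixed model with repeated measures, "where group allocation (TREATMENT and CONTROL) and time (6 and 12 months) will be treated as categorical values". No term for therapy group or therapist is named, nor any cluster-robust variance or related sensitivity analysis. Continuous secondary outcomes use the same method.

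Section 11 bases the sample size on a "clinically important group difference in the DHI of 11 points", "with a significance level of 0.05 and a power of 80% (SD 18.95), 47 participants are required per group". For gait it uses a "clinically important group difference in preferred gait velocity of 0.1 m/s" with "power of 80% (SD 0.15), 36 participants are required per group". Neither calculation mentions an ICC or a design effect. Section 16 says that between-group tests "will consist of two-sided tests with a 95% confidence level".

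**The concern.** Participants who spend eight two-hour sessions (16 hours) together, with the same fellow participants, may end up with more similar outcomes than participants treated separately. The clustering exists in one arm only, so this is a partially nested design. The repeated-measures part of the model handles correlation within a person over time. It does not handle correlation between people in the same therapy group.

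If that correlation is positive, the variance of the TREATMENT mean is larger than the model assumes. The estimated difference stays unbiased, but its confidence interval is too short and its p-value too small. This affects both primary outcomes. The Holm-Bonferroni step in Section 17 does not help, because it takes the individual p-values as valid. As planned, the report could not show whether the correlation was negligible.

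**Working it through.** **1. Reproduce the plan's figures under independence.** With n per arm = 2 × (SD × (1.960 + 0.842) / difference)²:

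- DHI: 2 × (18.95 × 2.802 / 11)² = 46.6, so 47.
- Gait: 2 × (0.15 × 2.802 / 0.1)² = 35.3, so 36.
- Total: 94 / 0.76 = 123.7, so 124, or 62 per arm with equal allocation.

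All three match Section 11, which confirms that no clustering allowance is built in.

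**2. Analysed group size.** Section 9 gives 5 to 8 per therapy group. Section 11 allows 24% dropout. Spread evenly, that leaves 5 × 0.76 = 3.8 to 8 × 0.76 = 6.1 analysed per group when 47 per arm are analysed. The number of therapy groups is about 62/8 to 62/5, so 8 to 12.

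**3. Formulas** (m = analysed group size; clustering in TREATMENT only; equal total variance in the two arms):

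- Design effect in TREATMENT: DE = 1 + (m − 1) × ICC
- Variance inflation of the arm difference: V = (1 + DE) / 2
- Type I error of the planned test: 2 × (1 − Φ(1.96 / √V))
- DHI power with a correct standard error: Φ(2.814 / √V − 1.96), where 2.814 = (11 / 18.95) × √(47/2)

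**4. One case in full.** Take m = 6.1 (6.08 unrounded) and ICC 0.05. DE = 1 + 5.08 × 0.05 = 1.254, V = 1.127 and √V = 1.062. Type I error = 2 × (1 − Φ(1.846)) = 6.5%. Power = Φ(2.651 − 1.96) = 75.5%.

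**5. Results with 47 analysed per arm, m from 3.8 to 6.1.** Every ICC here is an assumption.

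| ICC | True SE / model SE | Type I error | DHI power |
|---|---|---|---|
| 0 | 1.00 | 5.0% | 80% |
| 0.01 | 1.01 | 5.2–5.3% | 79–80% |
| 0.05 | 1.03–1.06 | 5.8–6.5% | 76–78% |
| 0.10 | 1.07–1.12 | 6.6–8.0% | 71–75% |

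Gait has more room at 47 per arm: (0.1 / 0.15) × √(47/2) = 3.232, which gives 90% power under independence. At m = 6.1 and ICC 0.10 it is Φ(3.232 / 1.120 − 1.96) = 82%. Its type I error is inflated as in the table.

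**6. Full retention (62 per arm, m from 5 to 8).** DHI power is 89% at ICC 0.01, 85–87% at 0.05 and 79–84% at 0.10. Type I error is 5.2–5.4%, 6.2–7.1% and 7.4–9.2%. Better retention therefore protects power but enlarges the groups and with them the error rate.

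**7. Simulation check.** A t-test that ignores clustering was simulated 40,000 times per setting, with m = 5 and 8 and with 47 and 62 per arm. It rejected in 6.1–7.2% of runs at ICC 0.05 and 7.2–9.2% at 0.10, in line with the formula.

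**The case against.** The strongest reply is that nothing in the documents shows that the ICC is material. Participants are randomised individually, the programme follows a manual, and outcomes are measured at about 6 and 12 months, after an 8-week course. At an ICC of 0.01 the error rate barely moves. TREATMENT participants who never attended a group would dilute the clustering further. This stands as a limit on the size of the effect, and it is why the consequence has to be stated conditionally. It does not answer the omission, because the plan neither justifies independence nor provides a way to check it.

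Two stronger readings should be resisted. A reader might infer that the same two therapists led every group. Section 9 says only that two physiotherapists led each session, and the argument does not need more than that. A reader might also pair 8 analysed per group with 47 per arm, which at ICC 0.10 gives 9.2% error and 68% power. That combination does not fit the plan's 24% dropout. With 8 analysed per group and 62 per arm the error rate is still 9.2%, but power is 79%.

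Blinding is a fair practical objection. Section 32 keeps compliance information from the biostatistician, and because only one arm has therapy groups, group identifiers would reveal the arms. With about 8 to 12 groups the variance component will also be poorly estimated and may come out as zero, in which case the estimate and standard error fall back to the planned ones. Both points shape the fix rather than remove the need for it.

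The separately published protocol was not available for this check. However, Section 32 makes the SAP the basis for all analyses of primary and secondary outcomes.

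**Conclusion.** The concern holds conditionally. The plan has clustering by design in one arm and no allowance for it in the primary model, the continuous secondary models or the sample size. Whenever the within-group ICC is above 0, the planned intervals are too narrow and the type I error exceeds 5%. The documents do not support saying that the error certainly exceeds 5%, because they give no ICC.

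Over an assumed ICC range of 0.01 to 0.10, with 47 analysed per arm, the inflation runs from trivial (5.2%) to appreciable (8.0%), and DHI power from about 80% down to 71%. With little dropout, power stays near or above 80%, but the error rate is not repaired.

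The figures assume equal variances, equal group sizes, a single-time-point contrast, every TREATMENT participant belonging to a group, and counts that refer to participants with observed outcomes. They use the plan's 0.05 level without the Holm step, and the power figures ignore the degrees of freedom lost through having few groups, so they are slightly optimistic. Treatment effect estimates are not biased by this. It is an inexpensive improvement that has most value if made before unblinding.

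**What to change.** **Section 27.** Before unblinding, specify a partially nested version of the mixed model for both primary outcomes and the continuous secondary outcomes. It needs a therapy-group random effect that acts only in TREATMENT, REML estimation, and Kenward-Roger or Satterthwaite degrees of freedom. Report the estimated ICC. Code every CONTROL participant, and every TREATMENT participant who never joined a group, as a singleton. Group membership should be recoverable, since the adherence definition in Section 19a already requires session attendance.

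**Blinding.** Either of two routes works, and the SAP should name one:

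- The blinded biostatistician writes and locks the code, and the uninvolved researcher who codes Groups A and B runs the clustered model.
- The clustered model is run directly after the blinded interpretation step, as a pre-specified analysis whose interval is reported with the primary result.

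**Section 11.** State that the 80% power assumes no within-group correlation. Section 9 describes delivery in the past tense, so this can only be a caveat, not a new sample size.

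**Cost.** Some SAP wording, one more variance component, slightly wider intervals, a component that is imprecisely estimated from about 8 to 12 groups, and care with the identifier coding. If the correlation is negligible, the result will hardly change and the report can show it.

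### Section 11 gives 80% power for DHI at an unadjusted 0.05, but under the Holm test in Section 17, 47 evaluable per group give about 72% to 79%, and the success rule is not stated

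*Combined protocol and SAP*

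**What the plan says.** Section 11 computes a sample size for each primary outcome separately. For DHI, with a difference of 11 points, it says that "with a significance level of 0.05 and a power of 80% (SD 18.95), 47 participants are required per group". For preferred gait velocity, with a difference of 0.1 m/s, it says "with a significance level of 0.05 and a power of 80% (SD 0.15), 36 participants are required per group". The larger number gives 94 in total, raised to 124 to allow for 24% drop-out.

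Section 16 says that between-group tests "will consist of two-sided tests with a 95% confidence level". Section 17 says that, because there are two primary outcomes, "the Holm-Bonferroni method will be used to control for a possible Type 1 error".

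The hypothesis, placed just before Section 3, is that the treatment group "will show significantly superior reduction in perceived dizziness related handicap in addition to increased preferred gait velocity", compared with the home-exercise group.

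No section says whether the trial succeeds on both outcomes or on either one. None gives a correlation between the outcomes, or any power other than the per-outcome 80%.

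**The concern.** Under Holm with two tests, the smaller p-value must pass 0.025, and the other is tested at 0.05 only if it does. A power computed at 0.05 for each outcome therefore cannot be the power of the planned procedure. DHI sets the sample size and has almost no margin at 47 per group, so any tightening takes it below 80%. The 24% drop-out allowance rests on the same 47.

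The second matter is interpretation. The hypothesis joins the two outcomes in one sentence, whereas Holm permits a claim on one outcome alone. Section 10 and the data management section require the authors to agree written interpretations of the blinded results. If only one outcome is significant, the rule for reading that result should already be fixed.

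**Working it through.** **Inputs.** From Section 11: DHI difference 11, SD 18.95; gait difference 0.1, SD 0.15; 80% power; 47 evaluable per group; 124 randomised, that is 62 per group. From Section 16: two-sided tests. From Section 17: Holm over two primary outcomes, read here as one test per outcome. Assumed: correlation between the two test statistics, signed so that improvement on both is positive, from 0 to 0.9.

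**Reproducing the plan.** n per group = 2(z_α + z_β)²(SD/d)², with z_β = 0.842.
- DHI at 0.05: 2(1.960 + 0.842)²(18.95/11)² = 46.6, so 47.
- Gait at 0.05: 2(1.960 + 0.842)²(0.15/0.1)² = 35.3, so 36.
- Drop-out: 94/0.76 = 123.7, so 124.

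All three figures reproduce, and only at two-sided 0.05. One-sided tests would give 37 and 28.

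**Per-outcome power at 47 per group.** The expected test statistic is (d/SD)√(47/2).
- DHI: 0.5805 × 4.848 = 2.814. Power at 0.05 is Φ(2.814 − 1.960) = 80.3%; at 0.025 it is Φ(2.814 − 2.241) = 71.7%.
- Gait: 0.6667 × 4.848 = 3.232. Power at 0.05 is Φ(3.232 − 1.960) = 89.8%; at 0.025 it is Φ(3.232 − 2.241) = 83.9%.

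**Power under Holm at 47 per group.** DHI is declared significant if it passes 0.025, or if it passes 0.05 and gait passes 0.025.
- Gait does not differ (independent statistics): 0.717 + (0.803 − 0.717) × 0.025 = 71.9%, about 72%.
- Gait differs by 0.1 m/s, correlation 0: 0.7165 + (0.8034 − 0.7165) × 0.839 = 78.9%.

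For other correlations the same events were evaluated under a bivariate normal distribution, with both planned effects present:

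| Power (%) at correlation | 0 | 0.3 | 0.5 | 0.7 | 0.9 |
|---|---|---|---|---|---|
| DHI, Holm | 78.9 | 78.5 | 78.3 | 78.2 | 78.5 |
| Gait velocity, Holm | 88.1 | 87.4 | 86.9 | 86.2 | 84.9 |
| Both outcomes, Holm | 71.7 | 73.2 | 74.6 | 76.2 | 78.2 |
| Both outcomes, each at 0.05 | 72.2 | 73.9 | 75.3 | 77.1 | 79.4 |
| At least one outcome, Holm | 95.4 | 92.7 | 90.6 | 88.2 | 85.1 |

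The third and fourth rows separate the causes. At correlation 0, requiring both outcomes already brings power to 0.803 × 0.898 = 72.2% with no adjustment. Holm takes off about half a point more, and about one point at correlation 0.9.

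**Drop-out that 124 can absorb while keeping 80% for DHI.**
- Worst case, DHI at 0.025: 2(2.241 + 0.842)²(18.95/11)² = 56.4, so 57 per group; 1 − 114/124 = 8.1%.
- Both planned effects real: 49 per group is the smallest number that gives at least 80% under Holm at each correlation in the table; 1 − 98/124 = 21.0%.
- Stated in Section 11: 24%.

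**Sensitivity.** With the t distribution in place of the normal, DHI at 0.025 is 70.3%, DHI under Holm with both effects 77–78%, and both outcomes 70–77%.

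**The case against.** The strongest reply is that Section 11 contains no arithmetic error. It openly gives a per-outcome power at 0.05, and 47, 36 and 124 are all correct on that basis. That stands: the fault is a mismatch with Section 17, not a miscalculation.

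A second reply is that the loss is small. Holm applies 0.025 only to the smaller p-value, and under the plan's assumptions gait has the larger expected statistic (3.232 against 2.814), so DHI will often be tested at 0.05. That also stands. If both planned effects are real, the shortfall for DHI is one to two points. The 72% for DHI applies when gait velocity does not differ.

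A third reply is that 47 is what remains after 24% drop-out. If all 62 per group are evaluable, DHI has 83.9% even at 0.025. This is true, but the allowance is stated precisely so that power survives that drop-out.

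A reader might infer more than the documents support:
- That the trial falls short of 80% under any success rule. It does not: power for at least one outcome is 85–95%.
- That Holm causes the 72% for both outcomes. Nearly all of that loss comes from requiring both. If both were required, testing each at 0.05 would already control the type I error.
- That the hypothesis is a formal both-outcomes rule. It states an expectation. Two primary outcomes, sized separately and tested with Holm, point to separate claims.
- That adjustment for baseline would restore the power. The documents give no baseline-to-follow-up correlation from which to judge this.

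**Conclusion.** The concern holds, in a limited form. The 80% power for DHI is calculated at a level that Section 17 replaces, and at 47 evaluable per group it is not delivered: 72% if gait velocity does not differ, 78–79% if it differs as assumed. Gait velocity stays above 80% in either case, at 84% tested at 0.025 and 85–88% under Holm if DHI also differs. The 24% drop-out allowance should read between about 8% and about 21% if 80% for DHI is to be kept.

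The success rule is left to inference. Holm implies outcome-by-outcome claims and the hypothesis can be read as joint, so the plan should say which applies.

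These figures rest on Section 11's differences and SDs, the normal approximation, and an assumed correlation of 0 to 0.9. They treat each outcome as a single test. Any further multiplicity from naming both 6 and 12 months in the primary endpoint was not examined here. The point does not imply inflation of the type I error or a need for more participants.

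**What to change.** Before the code is broken:
- Keep 124, and leave the existing calculation in Section 11 as the record of how the size was set.
- Add to Section 11 the power under Holm at 47 per group: DHI 72% to 79%, depending on whether gait velocity differs; gait velocity 84% to 88%, depending likewise on DHI; both outcomes 72–78%; at least one 85–95%. State the assumed correlation range.
- Give the matching drop-out tolerance for 80% power on DHI: about 8% in the worst case and about 21% if both planned effects are real.
- State one success rule that matches Section 17: superiority is claimed separately for each outcome that passes Holm.
- Word the hypothesis as two separate hypotheses, one for each outcome.

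The cost is SAP wording and a somewhat less favourable stated power. No participant numbers or analyses change.
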